Appendix B Handling of Human Biological Samples

Chain of custody

A full chain of custody is maintained for all samples throughout their lifecycle.

The investigator at each site keeps full traceability of collected biological samples from the participants while in storage at the centre until shipment or disposal (where appropriate) and records relevant processing information related to the samples whilst at site.

The sample receiver keeps full traceability of the samples while in storage and during use until used or disposed of or until further shipment and keeps record of receipt of arrival and onward shipment or disposal.

AstraZeneca or delegated representatives will keep oversight of the entire life cycle through internal procedures, monitoring of study sites, auditing or process checks, and contractual requirements of external laboratory providers

Samples retained for further use will be stored in the AstraZeneca-assigned biobanks or other sample archive facilities and will be tracked by the appropriate AstraZeneca Team during for the remainder of the sample life cycle.

Withdrawal of Informed Consent for donated biological samples

If a participant withdraws consent to the use of donated biological samples, the samples will be disposed of/destroyed/repatriated, and the action documented. If samples are already analysed, AstraZeneca is not obliged to destroy the results of this research.

Following withdrawal of consent for biological samples, further study participation should be considered in relation to the withdrawal processes outlined in the informed consent.

The investigator:

- Ensures participant's² withdrawal of informed consent to the use of donated samples is highlighted immediately to AstraZeneca or delegate
- Ensures that relevant human biological samples from that participant, if stored at the study site, are immediately identified, disposed of as appropriate, and the action documented
- Ensures that the participant and AstraZeneca are informed about the sample disposal

AstraZeneca ensures the organization(s) holding the samples is/are informed about the withdrawn consent immediately and that samples are disposed of or repatriated as appropriate, and the action documented and study site notified.

International Airline Transportation Association (IATA) 6.2 Guidance Document

LABELLING AND SHIPMENT OF BIOHAZARD SAMPLES

InternationalAirlineTransportationAssociation(IATA)(https://www.iata.org/whatwedo/cargo/dgr/Pages/download.aspx)classifiesinfectioussubstances into 3 categories: Category A, Category B or Exemptclassifiesinfectious

Category A Infectious Substances are infectious substances in a form that, when exposure to it occurs, is capable of causing permanent disability, life-threatening or fatal disease in otherwise healthy humans or animals. Category A pathogens are e.g., Ebola, Lassa fever virus. Infectious substances meeting these criteria which cause disease in humans or both in humans and animals must be assigned to UN 2814. Infectious substances which cause disease only in animals must be assigned to UN 2900:

Category B Infectious Substances are infectious Substances that do not meet the criteria for inclusion in Category A. Category B pathogens are e.g., Hepatitis A, C, D, and E viruses. They are assigned the following UN number and proper shipping name.

- UN 3373 Biological Substance, Category B
- are to be packed in accordance with UN3373 and IATA 650

Exempt - Substances which do not contain infectious substances or substances which are unlikely to cause disease in humans or animals are not subject to these Regulations unless they meet the criteria for inclusion in another class.

- Clinical study samples will fall into Category B or exempt under IATA regulations
- Clinical study samples will routinely be packed and transported at ambient temperature in IATA 650 compliant packaging (https://www.iata.org/whatwedo/cargo/dgr/Documents/DGR-60-EN-PI650.pdf)
- Biological samples transported in dry ice require additional dangerous goods specification for the dry-ice content

Appendix C Guidance related to assessments and procedures during COVID-19 pandemic

In view of the ongoing and emerging novel coronavirus (COVID-19) pandemic spreading worldwide, the safety and well-being of our study participants is of primary importance. To protect the safety and well-being of study participants, this section will provide guidelines on study assessments and procedures during this period.

- 1 ZS is a potassium binder acting in the gastrointestinal tract and is not absorbed. No additional risk from COVID-19 is expected due to ZS. Every effort should be made to follow the clinical study protocol (CSP). Participant safety is paramount, and the investigator should continue to reassess the risk/benefit of continued study involvement for each study participant.
- 2 Investigational study sites must comply with local public health rules.
- 3 If a study participant is suspected or diagnosed with COVID-19, they should follow the local guidance for COVID19 diagnosis, quarantine, and treatment procedures.
 - (a) Please accurately document all diagnoses, procedures, assessments, dosing interruptions, and sequelae in the eCRFs. All AEs/SAEs should be reported in line with instructions for safety reporting documented in the CSP.
 - (b) If a COVID-19 AE/SAE is reported, the investigator should determine whether the participant's investigational product should continue, be interrupted, or stopped in accordance with the CSP (section 3.9).
- 4 If a study participant is unable to attend clinic visits either due to quarantine for being infected with or suspected for COVID-19 or due to site closure for COVID-19, the investigational product should be discontinued, and every effort should be made to conduct safety assessment (e.g., potassium value and ECG measurement), this could be done at an alternative healthcare facility or by home visit if possible. Local lab results will not be collected or stored in the study database but will help the investigator to assess patient safety. The site staff should keep in close contact with the study participant(s), preferably through telephone calls, to maintain awareness of their status.

References:

https://www.fda.gov/media/136238/download

https://www.ema.europa.eu/en/implications-coronavirus-disease-covid-19-methodological-aspects-ongoing-clinical-trials

https://www.ema.europa.eu/en/news/guidance-sponsors-how-manage-clinical-trials-during-covid-19-pandemic

SIGNATURE PAGE

eGFR	Estimated Glomerular Filtration Rate
EOS	End of Study
FAS	Full Analysis Set
FAS-OLP	Full Analysis Set for the Open-Label Initial Phase
FAS-RTP	Full Analysis Set for the 28-day Randomized Treatment Study Phase
GFR	Glomerular Filtration Rate
GGT	Gamma-glutamyl transferase
Hb	Haemoglobin
HCG	Human chorionic gonadotropin

Abbreviation or special term	Explanation
HF	Heart failure
HL	Hy's law
ICH	International Conference on Harmonization
IP	Investigational Product
IPD	Important protocol deviations
ITT	Intent-to-Treat
LSMEAN	Least Square Mean
MedDRA	Medical Dictionary for Regulatory Activities
MI	Multiple imputation
OLP	Open-label initial phase
РО	Per Os
P-Renin	Plasma-Renin
РТ	Preferred Term
qd	Once daily
RAAS	Renin-Angiotensin-Aldosterone System
RBC	Red Blood Cell
REML	Restricted maximum likelihood method
RTP	28-day randomized treatment study phase
S-Aldo	Serum-Aldosterone
SAE	Serious Adverse Event
SAF	Safety Analysis Set
SAF-OLP	Safety Analysis Set for the Open-Label Initial Phase
SAF-RTP	Safety Analysis Set for the 28-day Randomized Treatment Study Phase
SAP	Statistical Analysis Plan
S-Ca	Serum calcium
S-HCO3	Serum bicarbonate
S-K	Serum potassium
S-Mg	Serum magnesium
S-Na	Serum sodium
S-PO4	Serum phosphate
SD	Standard deviation

Abbreviation or special term	Explanation
SOC	System Organ Class
TFL	Tables, Figures and Listings
TID	Three times a day
ULN	Upper limit of normal
VS	Vital Sign
WBC	White Blood Cell
WHO	World Health Organization
WHODrug	World health Organization Drug Dictionary
ZS	Sodium Zirconium Cyclosilicate

AMENDMENT HISTORY

CATEGORY Change refers to:	Date	Description of change	In line with CSP?	Rationale	
N/A	27-Sep-2021	Initial approved SAP	N/A	N/A	
Section 3.2.1.1.	04-Apr-2022	Definition of FAS-OLP updated to be in line with CSP	Yes	Update SAP to be in line with CSP	
Section 3.3	04-Apr-2022	Added convention used for rounding	NA	Consistency in outputs.	
Section 3.3.1.1	04-Apr-2022	 Removed timing for the two pre-dose measurements used to derive baseline for OLP. Added that baseline values can also be replaced. Added a sentence to confirm that measures taken on the same day as first IP are assumed to be pre-dose if time is missing. 	Yes	Clarifying the logic for imputing missing Clab values with i-STAT values.	
Section 3.3.1.2	04-Apr-2022	Added definition of 'on-treatment'	Yes	Clarifying the definition for consistency in outputs and summaries.	
Section 3.3.2.1	04-Apr-2022	Updated/added hypotheses for exponential rate of change.	No	Defining two time points (24/48 hr) as not all subjects will have 48h time point	
Section 3.3.3	04-Apr-2022	Table 2 (Analysis visit windows) updated.	Yes		
Section 3.3.5	22-Apr-2022	Section added to summarise how to handle missing S-K data	Yes	Consistency in how this handled for all efficacy outcomes.	
Section 4	04-Apr-2022	Removed quartiles from summary statistics	Yes	Quartiles are not required for the summaries.	
Section 4.1.5	04-Apr-2022	Serum potassium added as a baseline characteristic	NA	To improve assessment of baseline characteristics	
Section 4.1.7.1	04-Apr-2022	Definition of prior and concomitant added. Updated imputation of missing dates to coincide with Section 3.3.1.3	Yes	Clarifying the definition for consistency in outputs and summaries.	
Section 4.2.1.3	04-Apr-2022	Adding a time constraint to imputing missing values with i-STAT	Yes	Add an additional rule as to when it is appropriate to impute value.	

		Information added for the seed, number of burn-ins and variance structure for the multiple imputation		To provide further details on how the multiple imputation should be carried out.
Section 4.2.1.5	04-Apr-2022	Supplementary analysis of primary endpoint updated to be stop date of disallowed medication + 7 days.	Yes	To align the supplementary analyses for disallowed medications.
Section 4.2.1.6	04-Apr-2022	Added a specification of the number of observations required to conduct the subgroup analyses	Yes	To ensure enough observations to generate robust estimates.
Section 4.2.3.6	04-Apr-2022	Updated handling of missing data to be in line with the primary end point.	Yes	Clarifies that all RTP endpoint should be based on the imputed data.
Section 4.3.2	04-Apr-2022	Removed summary of AEs leading to discontinuation and most common AEs. Removed study specific AEs. Added summary by decreasing frequency.	Yes	To removed summaries of AEs that are not required and to update the AE table to present by decreasing frequency rather than selecting the most common to give a most robust overview of AEs.
Section 4.3.3	04-Apr-2022	Removed Hy's Law definitions and updated the elevated liver test summary	Yes	To condense the overview of elevated liver tests.
Section 4.3.6	04-Apr-2022	Added baseline versus maximum on-treatment summary for vital signs.	Yes	To provide additional analyses of the vital signs.
Section 3.3.1.3	12-Aug-2022	Added definition of 'treatment-emergent'	Yes	Clarifying the definition for consistency in outputs and summaries.
Section 4.2.2.1	12-Aug-2022	Updated list of time points at which the proportion of subjects who achieve normokalemia are assessed during the OLP	Yes	End of OLP timepoint was missing from list
Section 4.2.3.2	12-Aug-2022	Added derivation for the number of days subjects remain normokalemic	Yes	To provide further clarification on the logic of the derivation
Section 4.2.3.3	12-Aug-2022	Added additional description for the summaries required for time to hyperkalemia Yes To in or required		To align with requirements in output To align with requirements in output

STATISTICAL ANALYSIS PLAN D9480C00001 – ed. 3.0

Section 4.2.3.5	12-Aug-2022	Updated the minimum number of subjects required per subgroup analysis	Yes	To allow for a lower threshold for the subgroup analysis to be performed
Section 4.3.3.2	12-Aug-2022	Updated to use "treatment-emergent" in derivation description	Yes	To align with the definition of treatment-emergent added in Section 3.3.1.3
Section 4.3.6.2	12-Aug-2022	Updated to use "treatment-emergent" in derivation description	Yes	To align with the definition of treatment-emergent added in Section 3.3.1.3
Section 4.3.8.2	12-Aug-2022	Added that QTcF values above 450 ms at baseline should be summarised	Yes	To align with requirements in output
Section 3.3.1.4	18-Oct-2022	Added sentence to derivation of missing start/end dates for concomitant medications and AEs	Yes	To provide further logic on the imputation of missing dates.
Appendix A	24-Oct-2022	Updated IPD master file	Yes	To align with the most recent version of the IPD master file.

1 INTRODUCTION

The purpose of this document is to give details for statistical analysis of study D9480C00001 supporting the clinical study report. The reader is referred to the clinical study protocol (CSP) for details of study conduct.

This statistical analysis plan (SAP) contains a more detailed description of the analyses in the CSP for the Harmonize Asia study and is based on version 6.0 of the CSP.

This SAP applies to the phase 3, multicentre, prospective, randomized, double-blind, placebocontrolled study to investigate the safety and efficacy of ZS (sodium zirconium cyclosilicate), in patients with hyperkalemia (HARMONIZE Asia).

2 CHANGES TO PROTOCOL PLANNED ANALYSES

The text referring to a 2-sample t-test in section 8.5 of the CSP, ("Where applicable, comparisons between each active dose treatment group vs. placebo control group will be performed using a 2-sample t-test.") has been removed as needed in the SAP, as this referred to the descriptive tabulations of data, and this is no longer part of the planned descriptive tabulation of the study.

The structure of the model used for the main analysis of the primary endpoint has been amended to include visit, treatment, as well as visit-by-treatment interaction as fixed effects, to reflect the corresponding analysis done in the Harmonize Global study. In addition, rather than incorporating a random intercept within subject explicitly in the model, an unstructured marginal covariance matrix will be used. This is to provide better potential for achieving good model fit (note that a model with a random intercept within subject and an e.g. scaled identity as conditional covariance matrix is a special case of this approach).

The subgroup analysis of the primary endpoint has been amended to assess all subjects, rather than those with hyperkalemia (S-K \geq 5.1mmol/L). This reflects the corresponding analysis in the Harmonize Global study and aligns with the primary analysis of the primary outcome.

Change from baseline in the OLP has been amended to use a one-sample, two-sided, t-test instead of a paired, two-sided, t-test. This allows a comparison of the mean change from baseline to the null hypothesis of zero (i.e. no change from baseline) rather than assessing the difference between the paired observations. This also aligns with the approach taken in the Global Harmonize study.

To better reflect the Intent-to-Treat (ITT) approach defined to the efficacy analyses the secondary endpoint reading:

D9480C00001 - ed. 3.0

 "Proportion of subjects who remain normokalemic (as defined by S-K between 3.5-5.0 mmol/L, inclusive) during the 28-day randomized treatment study phase at Study Days 29/Exit"

has been changed to:

"Proportion of subjects who remain normokalemic (as defined by S-K between 3.5-5.0 mmol/L, inclusive) during the 28-day randomized treatment study phase at Study Days 29".

To reflect the flexibility of the duration of the open label phase introduced in the later versions of the CSP the endpoint reading:

- "Open-label phase mean change from baseline of S-K 48 hours after first dose of ZS 10g"

has been clarified to state:

"Open-label phase mean change from baseline of S-K to the end of OLP after first dose of ZS 10g".

To clarify the definition of the full analysis set in the open label initial phase, a subject is considered to have been registered into the OLP if they received at least 1 dose of study medication in the open label initial phase.

3 DATA ANALYSIS CONSIDERATIONS

3.1 Timing of Analyses

The primary analysis will be performed after database lock (DBL). No interim analysis is planned for this study.

3.2 Analysis Populations

Two main analysis populations are defined for two different periods of this study, the full analysis set (FAS) and the safety analysis set (SAF).

3.2.1 Full analysis set

All efficacy analyses, unless otherwise specified, will be performed using the full analysis set (FAS), which is based on ITT principle. That is, subjects allocated to a treatment group will be followed up, assessed, and analyzed as members of that group irrespective of their compliance with the planned course of treatment.

3.2.1.1 Full analysis set in Open-label initial phase (FAS-OLP)

For the open-label initial phase (OLP), the full analysis set will include all subjects who received at least 1 dose of study medication in the open-label initial phase.

3.2.1.2 Full analysis set in Randomized treatment study phase (FAS-RTP)

For the randomized treatment study phase (RTP), the full analysis set will include all subjects who are randomized to the 28-day randomized treatment phase, regardless of whether they took study medication or not.

In this set, subjects will be analyzed according to their randomized treatment assignment.

3.2.2 Safety analysis set

All safety analyses will be performed using the SAF. Safety analyses will be performed for each study phase, OLP and RTP.

3.2.2.1 Safety analysis set in Open-label period (SAF-OLP)

For the OLP, the safety analysis set will include all subjects who receive at least 1 dose of study medication in the initial phase.

3.2.2.2 Safety analysis set in randomized treatment study phase (SAF-RTP)

For the subsequent RTP, the safety analysis set will include all subjects in the FAS-RTP who receive at least 1 dose of study medication in the RTP. Subjects with erroneous treatment are analyzed according to that treatment only if they only received the erroneous treatment and none of the correct treatment. Subjects who receive more than one treatment are analysed according to their randomized treatment.

The analysis sets used for each outcome are provided in Table 1.

Table 1	1 Summar	v of outcome	variables a	nd analysis	populations
	- ~	,			populations.

Outcome variable	Analysis set
Efficacy data	
Primary endpoint/variables	FAS-RTP
Secondary endpoints/variables for open label	FAS-OLP
phase	
Secondary endpoints/variables for randomized	FAS-RTP
treatment phase	
Study population	
Demography characteristics	FAS-OLP and FAS-RTP
Baseline and disease characteristics	FAS-OLP and FAS-RTP
Important protocol deviations	FAS-OLP and FAS-RTP
Medical/surgical history	FAS-OLP and FAS-RTP
Concomitant medications	FAS-OLP and FAS-RTP
Study drug compliance	FAS-OLP and FAS-RTP
Safety data	
Exposure	SAF-OLP and SAF-RTP

Outcome variable	Analysis set
AEs	SAF-OLP and SAF-RTP
Laboratory measurements	SAF-OLP and SAF-RTP
Vital signs	SAF-OLP and SAF-RTP
ECG	SAF-OLP and SAF-RTP

3.3 General Considerations

All efficacy analyses will be performed separately for the open-label initial phase and the 28day randomized treatment study phase using their respective full analysis sets. Safety data will be separately summarized in a descriptive manner on the safety analysis sets for the OLP and the RTP, respectively.

All efficacy data will be listed by subject and will include S-K assessments data and efficacy response (achieve normokalemia) data. Study population listings will include disposition, protocol deviations, subjects excluded from efficacy analysis, demographic and baseline characteristics, and safety listings will include treatment compliance, adverse events, individual laboratory measurements, vital signs, physical examinations, and electrocardiograms (ECG).

Unless otherwise stated, percentages will be calculated out of the population total and for each treatment group and will be rounded to 1 decimal place. For continuous data, the mean and median will be rounded to one additional place compared to the original data, the standard deviation (SD) and standard error (SE) will be rounded to 2 additional places, and the minimum and maximum will be displayed to the same accuracy as the original data. If the number of decimal places of the original data is > 3, then the minimum and maximum will be assigned 3 decimal places, the mean and median 4 decimal places, and the SD and SE 5 decimal places.

Results of all statistical analyses will be presented using a 95% confidence interval (CI) and two-sided p-value, unless otherwise stated. All p-values will be presented to 3 decimal places. All p-values less than 0.001 will be presented as '< 0.001' and p-values greater than 0.999 will be presented as '> 0.999'.

SAS® version 9.4 or higher will be used for all analyses.

3.3.1 General Study Level Definitions

3.3.1.1 Definition of Baseline Efficacy Baseline

For the OLP: The baseline Serum Potassium (S-K) will be established on the OLP Study Visit 3 (pre-dose) by taking the mean of 2 different S-K values.

For the RTP: The baseline S-K, S-Aldo and P-Renin will be established based on the last prerandomization measurement for S-K, S-Aldo and P-Renin, respectively, obtained during the OLP.

If baseline S-K C-lab values are missing, the i-STAT data will be used to replace them as described in Section 4.2.1.3. Subjects with missing values at baseline will be excluded from the relevant efficacy analysis.

Safety Baseline

Safety analyses will be performed separately for OLP and RTP. For change from baseline tabulations (laboratory measurements, vital signs, ECG and weight) the baseline will be defined as follows:

For OLP: Baseline will be the last non-missing measurement taken prior to first IP administration during OLP. If a measurement was taken on the date of first IP administration and no time is recorded, it is assumed that the measurement was taken pre-dose and will be considered a candidate for baseline.

For RTP: Same as OLP baseline, i.e. the last non-missing measurement taken prior to first IP administration during OLP.

3.3.1.2 Definition of On-Treatment

For OLP: Any measurements that have an onset day on or after the date of first dose of openlabel study treatment and no later than the date of last dose of open-label study treatment + 1 day.

For RTP: Any measurements with an onset date more than one day after the day of last dose of open label study medication, and either on or after the day of first dose of randomized study medication, and no later than the day of last dose of study medication +1 day.

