4.3.1 Open-label initial phase Day 1 (Visit 3)

Patients will arrive in the morning, fasting (nothing by mouth except water for a minimum of 8 hours prior to potassium sample collection at the clinic).

The following assessment will be performed:

- Review and confirm the patient's eligibility for the study by assessing inclusion and exclusion criteria listed in Sections 3.1 and 3.2.
- Two potassium samples for assessment, using both i-STAT and the Central Laboratory, will be collected 60 minutes (± 10 min) apart.
- If either i-STAT potassium value is <5.1 mmol/L the patient will be declared a screen failure and withdrawn from the study.
- If both i-STAT values are ≥ 5.1 mmol/L the following samples will be collected:
 - A blood sample for standard assessment of hematology and clinical chemistry
 - Urine for standard assessment of urinalysis parameters including a pregnancy test if the patient is a woman of childbearing potential
- Obtain vital signs (pulse rate and blood pressure)
- Patient medical and surgical history including co-morbidities (over previous 6 months) will be obtained with the review of selection criteria
- Perform 12-lead Electrocardiogram (ECG)
- Perform a complete physical examination including weight, see Section 5.2.2;
- Review and record the concomitant medications and AEs/SAEs

Note: The above procedures should be performed within 1 day of the first administration of study drug and before any IP administration.

Patients who meet all inclusion/exclusion criteria will be entered into the trial and the following procedures will take place:

- The site will access the IVRS/IWRS and the system will assign the patient an openlabel initial phase IP kit
- The first doses of study IP will be administered as a slurry/suspension in water. The patient will be shown/instructed on how to mix and administer the IP
- 1 hour (± 15 min) after dose administration a blood potassium sample (i-STAT and Central Laboratory) will be collected, following which the patient is allowed to break the fast
- Two additional blood potassium samples (i-STAT and Central Laboratory) will then be taken at 2 and 4 hours (±15 min) after dose administration.

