3.3.3 Visit Window

In the absence of nominal visits, visits windows will apply. Measurements will be assigned to exhaustive visit windows based on study day such that measurements taken at any time point can be accounted for and used in summaries and/or analyses. If an unscheduled visit occurred in the same window, then the measurement from the scheduled visit will be used in the analysis. If there are multiple unscheduled visits in the same visit window, then the visit closest to the scheduled visit day will be used. If there are multiple records on the same day the last measurement will be used.

- For summaries showing the maximum or minimum values, the maximum/minimum value recorded on treatment is used (regardless of where it falls in an interval).
- Listings display all values contributing to a time point for a subject.
- For visit-based summaries
 - If there is more than one scheduled value per subject within a time window then the closest value to the scheduled visit date is summarized. If the scheduled values are equidistant from the nominal visit date, then the earlier value is used. Data listings will highlight the values used in the summary table, wherever feasible.
 - Note: in summaries of extreme values (i.e. when assessing the minimum/maximum on-treatment values), all post baseline values collected are used including those collected at unscheduled visits regardless of whether or not the value is closest to the scheduled visit date and appears in the corresponding visit-based summary.

Visit windows are described in Table 2.

Study Visit (Target Day)	Nominal Target Day	Study Visit Window (Days)		
		Lower	Upper	
Pre Screening Phase and Screening				
Phase ¹				
Visit 2 (Sereening)				
Open Label Phase			1^{1}	
OLP-Day 1	1	1	1	
OLP-Day 2 ²	2	2	2	
OLP-Day 3 ³	3	3	3	
End of OLP (24 hours or 48	2 or 3			
hours) ⁴				
End of Study Visit (OLP-Day 9) ⁵	9	4	16	
Randomized Treatment Phase				
Randomization (RTP-Day 1)	1	1	1	
Visit 6 (RTP-Day 2)	2	2	2	
Visit 7 (RTP-Day 5)	5	3	6	
Visit 8 (RTP-Day 8)	8	7	9	
Visit 9 (RTP-Day 12)	12	10	13	
Visit 10 (RTP-Day 15)	15	14	17	
Visit 11 (RTP-Day 19)	19	18	20	
Visit 12 (RTP-Day 22)	22	21	24	
Visit 13 (RTP-Day 26)	26	25	27	
Visit 14 (RTP-Day 29)	29	28	31	
End of Study Visit (RTP-Day 35) ⁶	35	32	43	

Table 2 Time windows for allocation of data to visits for statistical analysis

1. The screening phase lasts up to the date and time when the open label initial phase is initiated, i.e. date and time of the first dose.

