4.3.6.2 Presentations

Summary statistics for vital signs will be calculated for absolute values and change from baseline to each subsequent planned visit where applicable. For each summary, the number of non-missing observations, mean, median, standard deviation, minimum, and maximum will be presented by treatment group for each study phase (OLP and RTP).

Baseline versus maximum value on treatment shift table will be provided for all vital sign parameters.

Any treatment-emergent, abnormal vital signs will be summarized and listed for the safety analysis set by treatment group for each study phase (OLP and RTP).

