4.3.8.2 Presentations

Overall ECG evaluations will be presented in a shift table showing baseline classification against last on-treatment (OLP and RTP) classification, by treatment group.

The following ECG variables will be descriptively summarized by treatment group and visit to include change from baseline to each subsequent visit: ECG mean heart rate, P wave duration, PR interval aggregate, QRS duration aggregate, QT interval aggregate and QTcF interval aggregate. The summaries will be presented for OLP and RTP, separately.

A listing of subjects with overall ECG evaluation reported as abnormal or borderline abnormal will also be provided.

QTc intervals

Number and percentage of subjects for QTcF for the following categories will be provided for OLP and RTP, by treatment group.

• QTcF value above 450 ms at baseline (>450 ms, 480 ms and > 500 ms):

- QTcF value above 450 ms at any time during treatment (>450 ms, 480 ms and > 500 ms):
- QTcF increase by more than 30 ms at any time during treatment (>30 ms, >60 ms and >90 ms)
- QTcF value above 450 ms and QTcF increase [a] by more than 30 ms at any time during treatment [(value > 450 ms and increase >30 ms and (value > 500 ms and increase >60 ms)]
- QTcF decrease by more than 30 ms at any time during treatment (>30 ms, >60 ms and >90 ms).

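### The open-label on-treatment window opens on the calendar date of first dose, so a pre-dose ECG dated that day can be counted as a during-treatment QTcF value

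*SAP*

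**What the plan says.** **On-treatment, open-label phase (SAP 3.3.1.2).** The window starts with "Any measurements that have an onset day on or after the date of first dose of openlabel study treatment" and ends "no later than the date of last dose of open-label study treatment + 1 day". There is no clock-time condition and no requirement that the value follow the dose.

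**Safety baseline (SAP 3.3.1.1).** "Baseline will be the last non-missing measurement taken prior to first IP administration during OLP". For a value dated on the first-dose day with no time recorded, "it is assumed that the measurement was taken pre-dose and will be considered a candidate for baseline".

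**When baseline is taken.** Protocol 4.3.1 lists the Day 1 blood and urine samples, vital signs, ECG and physical examination, and adds: "The above procedures should be performed within 1 day of the first administration of study drug and before any IP administration". Dosing follows in the same visit description. Table 1 note 11 of the protocol and SAP 4.1.5.1 also allow baseline to be collected up to one day before the first dose.

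**Outputs.** SAP 4.3.8.2 asks for patients with "QTcF value above 450 ms at any time during treatment" (steps at 450, 480 and 500 ms), listed straight after the same steps at baseline. SAP 4.3.6.2 says: "Baseline versus maximum value on treatment shift table will be provided for all vital sign parameters". Similar maximum-value outputs are planned for urinalysis (4.3.4.2) and for ALT and AST against bilirubin (4.3.3.2).

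**Extreme values (SAP 3.3.3).** One bullet takes the maximum or minimum recorded on treatment. A later note on the same summaries says "all post baseline values collected are used including those collected at unscheduled visits".

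**The concern.** A date-only window cannot separate a pre-dose record from a post-dose record on the day of first dose. A patient whose only QTcF above a threshold was recorded before any study drug would still be counted in the during-treatment row.

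QT is a stated interest of this trial. Exclusions 13 to 16 were added in protocol version 5.0 because of a possible QT effect of ZS, and protocol 3.9 sets QTc stopping limits. Entry is barred only above 550 ms, so a purely pre-drug value between 500 and 550 ms could reach the row above 500 ms. The open-label QT table would then overstate how many patients crossed a threshold while on drug. Two programmers following the same SAP could also produce different tables, depending on whether they carried the 3.3.3 note across.

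**Working it through.** The plan states no figure to reproduce here. The check compares the definitions and then illustrates the size.

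**Step 1. Which rule captures which record**

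| Record | Safety baseline (3.3.1.1) | Open-label on-treatment (3.3.1.2) | Post baseline (3.3.3 note) |
|---|---|---|---|
| Baseline, dated the day before first dose | Yes | No | No |
| Baseline, pre-dose on the first-dose date, timed or untimed | Yes | **Yes** | No |
| After first dose, up to last open-label dose date + 1 day | No | Yes | Yes |

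The middle row is the problem. The randomized-phase window usually avoids it: it starts more than one day after the last open-label dose, so a patient dosed up to the day before randomization does not bring the randomization-day pre-dose record into it.

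**Step 2. Which outputs are exposed**

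- Absolute QTcF threshold counts: exposed. SAP 4.3.8.2 does not refer to the 3.3.3 note.
- Maximum summaries for vital signs, urinalysis, ALT and AST: exposed only if the 3.3.3 note is not applied.
- Overall ECG shift to last on-treatment classification: touched only for a patient with no post-dose open-label ECG, whose baseline would be compared with itself.
- Treatment-emergent summaries: not affected, because SAP 3.3.1.3 requires a normal baseline.
- QTcF increase and decrease categories: not affected, because the baseline record has change 0. The combined categories are also safe. If baseline exceeds the threshold and a later value is higher still, that later value exceeds it too.
- Open-label hypokalemia counts: not affected in practice, because entry needs two i-STAT values of at least 5.1 mmol/L.

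**Step 3. Size for QTcF above 450 ms**

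Input from the documents: N = 280 entering the open-label phase (protocol 8.2). Assumed, because the documents do not give them: baseline and post-dose QTcF bivariate normal; mean m = 425 to 430 ms; SD 25 to 30 ms; correlation r = 0.6 to 0.9; mean change d = 0 to +5 ms; one post-dose ECG per patient; same-day share s unrelated to QTcF.

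Overcount = N × s × P(baseline > 450 and post-dose ≤ 450)

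With s = 1:

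| m, SD, r, d | Post-dose only | Baseline or post-dose | Overcount |
|---|---|---|---|
| 425, 25, 0.9, +5 (smallest) | 280 × P(Z > 0.80) = 59.3 | 66.5 | 7.2 |
| 430, 30, 0.7, 0 | 280 × P(Z > 0.667) = 70.7 | 98.7 | 28.0 |
| 430, 30, 0.6, 0 (largest) | 70.7 | 103.2 | 32.5 |

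The range is about 7 to 32 patients, or 7.2/280 = 2.6 to 32.5/280 = 11.6 percentage points. The overcount is proportional to s, so s = 0.5 gives about 4 to 16 and s = 0 gives none.

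**Step 4. Must the during-treatment count be at least the baseline count?**

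A separate simulation used 1,500 runs of 280 patients: mean 430 ms, between-patient SD 22, within-patient SD 12, one post-dose ECG for all and a second for 25%. With all baselines same-day and no true change, the literal count averaged 84.9 against 65.0 for post-dose values only, an overcount of 19.9. With a true change of −10 ms:

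| Same-day share | Baseline count | Literal during-treatment count | Post-dose only | Runs with literal count below baseline count |
|---|---|---|---|---|
| 100% | 59.8 | 69.2 | 36.4 | 0% |
| 90% | 59.5 | 65.4 | 35.8 | 3% |
| 75% | 59.7 | 60.8 | 36.1 | 34% |
| 50% | 59.6 | 52.5 | 36.2 | 92% |
| 0% | 59.3 | 36.1 | 36.1 | 100% |

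The floor at the baseline count holds patient by patient for same-day baselines. It holds for the whole table only when every baseline is same-day.

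**The case against.** The strongest reply is that SAP 3.3.3 already deals with this. Its note is specific to on-treatment extremes and restricts them to post-baseline values, and a specific rule normally narrows a general window. A QTcF above 450 ms at some time on treatment is the same thing as an on-treatment maximum above 450 ms, so a careful programmer could apply the note there too. The open-label phase is also single-arm and these counts are descriptive, with no comparator or decision rule. The change-from-baseline QT categories are intact.

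Much of this stands. The note reasonably protects the vital-sign, urinalysis and liver-test maxima, so a claim that those tables cannot show improvement would go too far. For the QTcF threshold counts the reply rests on inference: SAP 4.3.8.2 does not invoke the note, and 3.3.1.2 as worded admits the pre-dose record.

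A reader might also infer that every patient's baseline is double-counted and that the during-treatment count can never fall below the baseline count. The documents do not support that, because baseline may be dated the day before dosing and such a record lies outside the window.

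**Conclusion.** The definition is wrong as written for measurements, though its reach is narrow. Followed literally, SAP 3.3.1.2 counts same-day pre-dose values as on-treatment, inflates the open-label absolute QTcF counts and sits unreconciled with the note in 3.3.3. The other outputs are either unaffected or protected if that note is applied.

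The size cannot be fixed from the documents. The Step 3 range depends on the assumed QTcF distribution and on the same-day share; extra post-dose ECGs, which some patients will have, would reduce it. The visit flow in protocol 4.3.1 makes same-day baselines the expected case, but the actual share is not stated. The point should be corrected. It does not bear on the primary or any other efficacy analysis.

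**What to change.** In SAP 3.3.1.2, open-label phase, for ECG, laboratory, urinalysis and vital-sign records:

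- define on-treatment as taken after the first open-label dose, by clock time or protocol time point, keeping the present end of the window;
- exclude any pre-dose record and any record used as baseline, including untimed records on the first-dose date, which 3.3.1.1 already treats as pre-dose;
- state in 3.3.3 or 4.3.8.2 that the post-baseline rule also governs the QTcF threshold counts.

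Keep the date rule for adverse events. SAP 4.3.2.2 adopts it deliberately as a worst-case allocation, because events before and after intake cannot be told apart.

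The cost is a short SAP clarification and one programming condition. It needs no new data and no change to trial conduct.
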